9.7. Vital Signs and Physical Evaluations

Vital sign measurements included systolic blood pressure, diastolic blood pressure, pulse, and oral temperature. Vital signs were assessed at Day 0 and, Day 56. A targeted physical exam is performed at the screening visit, and if necessary at follow up visits. The following body systems will be assessed: Abdomen, Cardiovascular/heart Extremities, General Appearance, HEENT, Lymph nodes, Musculoskeletal, Neck, Neurological, Pulmonary/Chest, and Skin Since the evaluations are symptom-driven from enrollment to the end of follow-up, subject listings of vital signs and targeted physical exam findings will be provided ([Listing 19](#) and [Listing 20](#)).

9.8. Concomitant Medications

Summaries of medications that were started prior to dosing and continuing at the time of dosing as well as medications that were starting during dosing or during follow up will be presented by WHO Drug Anatomical codes (ATC) level 1 and level 2 and actual treatment group for subjects in the Safety population ([Table 112](#)) and by site ([Table 113](#)).

Individual subject listings will be presented for all concomitant medications ([Listing 21](#)).

Summaries of substance treatment will be summarized by site and treatment group in [Table 114](#) and [Table 115](#). A subject listing will be provided in [Listing 22](#).

10. IMMUNOGENICITY

The secondary objective of this study is to evaluate the immunogenicity of the AdCh3NSmut1 and MVA-NSmut vaccines compared to placebo when administered to HCV-uninfected IDUs. To assess this, the frequency of positive cell mediated immune responses within 14 days after the last vaccination will be compared between the vaccine and placebo groups.

The primary assay to monitor vaccine immunogenicity is the IFN- γ ELISpot, which will be performed at time points indicated in the study visit flow chart in Section 4.5. Samples are run in triplicate; thus, each pool of peptides will have three responses. In addition, the ELISpot data is reported from the lab in spots per 200,000 PBMC. Thus, in calculating an individual's pool-specific response, the raw data for a pool will be multiplied by five and then averaged across the triplicates. The negative control, DMSO, is also analyzed (in triplicate). Thus, to correct for background for each individual, the average of the triplicate DMSO responses will be subtracted from each of the averaged pool responses. All analyses of ELISpot data will use the averaged and background-corrected responses. Pool-specific summaries will use the following labels: NS3p, NS3h, NS4, NS5a, NS5bI, and NS5bII (these labels correspond to the following peptides, respectively: NS3 protease aa 1027-1349, NS3 helicase aa 1339-1661, NS4 aa 1655-1977, NS5a aa 1971-2425, NS5bI aa 2415-2725, and NS5b aa 2715-3011). In addition, for Visit 26 summaries, the following five pools will also be included in pool-specific summaries: Core, E1, E2, p7, and NS2. These additional pools will not be used for summaries that combine pools.

A positive immune response is defined by two criteria:

- i. more than 48 spot forming cells per million PBMC;
- ii. at least three times the mean background spots per million PBMC found in ELISpot wells containing cells and peptide diluent (DMSO) [13,14,15].

An individual will be considered a responder if a positive response to at least one in 6 mixtures (pools) of peptides is detected. The number of responders and response rate with associated 95% confidence interval will be summarized by treatment group (Table 116).

A number of secondary summaries of the immunogenicity data will be generated. Some of the summaries will be generated by treatment group whereas others will only be generated for subjects in the vaccine group. The summaries will be generated separately for HCV negative and HCV positive subjects. The following tables, figures, and listings will be generated:

- Geometric mean and geometric mean fold rise ELISpot responses (across all peptide pools) by study day and treatment group (Table 117 and Table 118)
- Geometric mean and geometric mean fold rise ELISpot responses (across positive peptide pools) by study day and treatment group (Table 119 and Table 120)
- Total number of positive peptide pools by study day and treatment group (Table 121 and Table 122)
- Maximum ELISpot response (across positive peptide pools) by treatment group (Table 123).
- Individual and Median ELISpot Responses (across all peptide pools) by Study Day [excluding uninfected placebo recipients] (Figure 13, Figure 14, and Figure 15).
- Boxplots of ELISpot Response to Peptide Pools at Study Day 63 [excluding uninfected placebo recipients] (Figure 16).

- Number of Positive Peptide Pools by Study Day [excluding uninfected placebo recipients] ([Figure 17](#)).
- Boxplots of Maximum ELISpot Responses to Peptide Pools [excluding uninfected placebo recipients] ([Figure 18](#)).

A listing of individual immunogenicity data will be provided in [Listing 23](#) .

11. OTHER ANALYSES

In the March 25, 2013 Data and Safety Monitoring Board summary report for DMID Protocol 10-0069, the early discontinuation rate for the study was observed to be higher than anticipated in the protocol. During the March 2013 DSMB teleconference, the DSMB members recommended that behavior data be analyzed against dropouts to determine if there is a difference in behavior between subjects who remain in follow-up or complete the study and subjects who discontinue the study early. A risk behavior assessment report was generated to address the DSMB's recommendation and presented at the April 29, 2014, May 26, 2015, and October 2016 DSMB teleconferences. No differences in behavior between subjects who remained in follow-up or completed the study and subjects who discontinued the study early were identified. The summaries presented at the DSMB teleconferences will be included in the final report to re-assess whether there are differences in risk behavior between subjects who remain in follow-up or completed the study and subjects who discontinued the study early.

The behavior data focus on injection drug use practices collected in the Behavioral Assessment Questionnaire administered in 90 day intervals throughout the duration of the planned follow-up period for the study. The behavior data presented in the final report will be grouped in figures by related Behavioral Assessment Questionnaire questions. The hypothesis tests performed for the risk behavior analyses are for illustrative purposes and not for making definitive claims.

The tables and figures to be generated for the final report will follow a subset of the shells provided in the Risk Behavior Assessment Shells (v1.0, September 2013). Each table and figure will be generated for all enrolled subjects, and separately for each treatment group. Below summarizes the subset of tables and figures to be included in the final report using the numbering in the Risk Behavior Assessment Shells document. The figures will be combined into paneled figures in the final report.

A table will be generated which summarize behavioral assessment completion by visit (Table 1 in Risk Behavior Shells document).

Tables and figures will be generated which summarize baseline behavior data by site and by study status. Each set of related questions in the questionnaire are summarized in different subfigures. Denoted in the figures are the questions with statistically significant results for the following three sets of hypothesis tests:

- For dichotomous responses: whether the proportion of 'Yes' respondents is the same across site using Fisher's Exact Test (significance level of 0.05). The null hypothesis is that the proportion of 'Yes' respondents is the same across site. For continuous responses: whether the distribution of responses is equal across site using the Kruskal-Wallis Test (significance level of 0.05). The null hypothesis is that the distribution of responses is equal across site
- For dichotomous responses: whether the proportion of 'Yes' respondents is the same across study status within each site using Fisher's Exact Test (significance level of 0.05). The null hypothesis is that the proportion of 'Yes' respondents is the same across study status. For continuous responses: whether the distribution of responses is equal across study status within each site using the Wilcoxon test (significance level of 0.05). The null hypothesis is that the distribution of responses is equal across site.
- For dichotomous responses: whether the odds ratio between study status is the same at each site using the Breslow Day test (significance level of 0.05). The null hypothesis is that the odds ratios at each site are all equal. For continuous responses: whether the distribution of responses is the same across study status at both sites using Van Elteren's test (significance level of 0.05). The null hypothesis is that the distribution of responses at each site are all equal.

(See Table 2.1 and Table 2.2 in Risk Behavior Shells Document and [Figure 41](#) and [Figure 42](#) in this SAP).

Additional figures will summarize behavior data for each study visit, by study status and at all study visits in which a subject continued follow-up or completed the study after conducting the behavioral assessment. The goal of the latter is to determine if there was a change in behavior prior to early termination as compared to all other timepoints in the study. Each question will be summarized in a separate figure (See all Figures in Risk Behavior Shell document).

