QM	Quality Management
RBV	Ribavirin
RCA	Replication Competent Adenovirus
RIBA	Recombinant Immunoblot Assay
RNA	Ribonucleic Acid
SAE	Serious Adverse Event/Serious Adverse Experience
SDCC	Statistical and Data Coordinating Center
SGPT	Serum Glutamic Pyruvic Transaminase
SIV	Simian Immunodeficiency Virus
SFC	Spot-Forming Cell
SMC	Safety Monitoring Committee
SMS	Short Message Service
SOP	Standard Operating Procedure
SUSAR	Suspected Unexpected Serious Adverse Reaction

TRAP	Thrombospondin-Related Adhesion Protein
UCSF	University of California San Francisco
UK	United Kingdom
UNM	University of New Mexico
US	United States
vp	Virus Particles
WBC	White Blood Cell
WHO	World Health Organization

LIST OF TABLES

LIST OF FIGURES

[figure not shown]
Figure 1.	The nonstructural region of the hepatitis C virus encoded by the vaccine	7
Figure 2.	The phylogenetic tree of adenovirus' hexons	9
Figure 3.	Kinetics of IFN-y ELISpot responses over time1	2

PROTOCOL SUMMARY

Title:	A Staged Phase I/II Study, to Assess Safety, Efficacy and Immunogenicity of a New Hepatitis C Prophylactic Vaccine Based on Sequential Use of AdCh3NSmut1 and MVA-NSmut
Phase:	1/11
Design:	 Double-blinded, randomized, placebo-controlled two stage study. Stage 1: 68±4 evaluable subjects Arm A: 34±2 evaluable subjects; 1 dose AdCh3NSmut1 2.5 x 10¹⁰ vp at Day 0, and 1 dose MVA-NSmut 1.8 x 10⁸ pfu at Day 56 Arm B: 34±2 evaluable subjects; 1 placebo dose at Day 0, and 1 placebo dose at Day 56 Stage 2: 472±4 subjects Enrollment will be initiated after an interim analysis of the Stage 1 safety and immunogenicity data. Arm A: 236±2 subjects; 1 dose AdCh3NSmut1 2.5 x 10¹⁰
	vp at Day 0, and 1 dose MVA-NSmut 1.8 X 10 ⁸ pfu at Day 56 Arm B: 236±2 subjects; 1 placebo dose at Day 0, and 1 placebo dose at Day 56
	Total number of subjects: 540±8 subjects
Population:	Males and females negative for HCV antibodies and HCV RNA at screening, active injection drug users at high risk for hepatitis C, and 18 to 45 years old.
Number of Sites:	Three Sites (University of California San Francisco; The Johns Hopkins University, Baltimore; University of New Mexico, Albuquerque)
Study Duration:	Approximately 63 months

Subject Participation Duration:	12 months to 29 months. Non-viremic subjects will be followed for 20 months; subjects who are viremic will be followed for 9 months after detection of HCV (up to month 29).	

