6.4. Covariates and Subgroups

As described in Section 4.4.2, the randomization of treatment assignments and the primary analysis will be performed as stratified by gender and IL28B status. Randomization is also stratified by clinical site, however given that the University of New Mexico was added late in enrollment (first enrollment 16 November 2015); stratifying analyses by site in addition to gender and IL28B may result in insufficiently sized strata. Thus, efficacy analyses will not be stratified by site and safety analyses will be separately stratified by site.

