 # denotes that the Breslow Day Test for the test of homogeneity resulted in a p-value < 0.05.

Figures with similar format:

Figure 42: Summary of Baseline Injection Drug Use by Treatment Group and Discontinuation Status - All Enrolled Subjects Completing at Least One Behavioral Questionnaire

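### SAP 11 gives Van Elteren's test a null hypothesis that it does not test, and its reference to two sites is out of date

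*SAP*

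**What the plan says.** SAP section 11 describes three sets of tests on baseline behavior data. Each set has one test for yes/no items and one for continuous items, and significant results are to be marked in the figures.

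In the third set, yes/no items get the Breslow-Day test, with the null: "The null hypothesis is that the odds ratios at each site are all equal". Continuous items get a test of "whether the distribution of responses is the same across study status at both sites using Van Elteren's test", followed by this null: "The null hypothesis is that the distribution of responses at each site are all equal".

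The notes under Figure 41 (SAP Appendix 2) define three symbols. Two are for Fisher's exact test, and the third "denotes that the Breslow Day Test for the test of homogeneity resulted in a p-value < 0.05". No symbol is defined for any test of a continuous item. Figure 42 follows the same format.

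The Protocol Summary lists three sites. SAP 6.4 dates the third site's first enrollment to 16 November 2015, whereas section 11 relies on "shells provided in the Risk Behavior Assessment Shells (v1.0, September 2013"). Section 11 also says that its tables and figures cover all enrolled subjects, and that its hypothesis tests are illustrative only.

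**The concern.** The question sentence, the stated null and the place in the list point to different hypotheses. The question sentence is about study status. The null is about sites. The pairing with Breslow-Day suggests a third question: whether the status difference is the same at every site. Van Elteren's test addresses only the first of these.

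A programmer could run the named test and report it against the printed null. A reader would then take a significant result as evidence that sites differ, or that the dropout difference varies by site, when it shows a status difference in a common direction. Section 11 exists because early discontinuation was higher than anticipated and the DSMB asked whether those who leave behave differently. SAP 6.5 censors subjects at missing follow-up, so a misread result here would feed into a discussion of whether that censoring is related to risk.

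**Working it through.** The plan gives no figure to reproduce for this point. The check has three parts.

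**1. The three sets side by side (SAP 11)**

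| Set | Yes/no item | Continuous item | Null printed for the continuous test | Match? |
|---|---|---|---|---|
| 1 | Fisher, across sites | Kruskal-Wallis, across sites | equal across sites | yes |
| 2 | Fisher, across status within site | Wilcoxon, across status within site | equal across sites | no; should be across study status |
| 3 | Breslow-Day, odds ratios equal across sites | Van Elteren, across status | equal at each site | no |

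Sets 1 and 2 each pair two tests of one question. Set 3 does not.

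**2. What Van Elteren's test measures**

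At site s, let n be the number of subjects, m the discontinuers, k = n − m the others, and W the rank sum of the discontinuers within that site. Then

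Z = Σ [W − m(n+1)/2]/(n+1) ÷ √( Σ mk/[12(n+1)] ).

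Ranks are taken within site, so a difference between sites in the level of response drops out. The test cannot address the printed null. If θ is the probability that a discontinuer's value exceeds another subject's value at that site, the mean of each numerator term is mk(θ − 0.5)/(n+1). These terms are summed with their signs, so equal effects add and opposite effects cancel.

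Worked case. Assumptions: sites of 240, 240 and 60, 35% discontinued, normal responses, shift 0.4 SD.

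- θ = Φ(0.4/√2) = 0.6114, so θ − 0.5 = 0.1114.
- Each large site: m = 84, k = 156, mk/(n+1) = 13,104/241 = 54.37.
- Small site: m = 21, k = 39, mk/(n+1) = 819/61 = 13.43.
- Sum = 122.17, and the denominator is √(122.17/12) = 3.19.
- Same shift at all sites: mean Z ≈ 0.1114 × 122.17/3.19 = 4.27, so power ≈ Φ(4.27 − 1.96) = 99%.
- Shifts of +0.4, −0.4 and 0: the numerator is 0.1114 × (54.37 − 54.37 + 0) = 0, so rejection stays near 5%.

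**3. Simulation**

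There were 5,000 data sets per scenario, two-sided alpha 0.05. The total of 540 is the target enrollment (SAP 5). The site splits (240/240/60 or 180/180/180), discontinuation of 20%, 35% or 50%, normal responses and the shifts are assumptions. The comparator is a homogeneity test: Cochran's Q on the three within-site Mann-Whitney effects, Q = Σ w(θ̂ − θ̄)², with w the inverse variance and 2 df.

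| Shift in discontinuers at the three sites (SD) | Van Elteren rejects | Homogeneity Q rejects |
|---|---|---|
| 0, 0, 0 | 4–5% | 5–6% |
| 0.4, 0.4, 0.4 | 95–99.6% | 4–7% |
| +0.4, −0.4, 0 | 4–5% | 76–98% |
| 0, 0, 0.8 | 12–15% (third site 60); 64–83% (third site 180) | 57–97% |

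The worked case agrees with its simulated counterparts (99.0% and 4.8%). A separate simulation used assumed sites of 200/200/90, about 30% discontinued and 2,000 data sets per scenario. With a status-by-site interaction test on ranks as comparator, the result was the same. For a common 0.4 SD shift, Van Elteren rejected in 98% and the interaction test in 5%. For opposite shifts at the two large sites, the figures were 4% and 90%. With no shift they were 5.0% and 6.0%.

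**The case against.** Four stronger readings are tempting, and the documents do not support them.

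- *The SAP uses Van Elteren as a homogeneity test.* It never says so. A reader infers this from the pairing with Breslow-Day and from the printed null. The question sentence, read alone, is close to what the test does. The Wilcoxon item in the second bullet has a similar slip in its null, so a drafting error is at least as likely as a wrong choice of test.
- *The third site is left out.* No text excludes it. Section 11 covers all enrolled subjects, and most by-site shells, such as Tables 28 and 31, have three site columns. The two-site wording fits shells written before that site opened. The Table 103 shell still names only two sites, which shows that such wording survives elsewhere, not that data will be dropped.
- *The homogeneity flags are wrong.* The only flag with that label is Breslow-Day for yes/no items, which is a valid homogeneity test. The gap is that continuous-item tests have no symbol in the figure notes.
- *The dropout check fails.* The second bullet compares study status within each site, and further figures follow behavior by visit and before early termination. Opposite effects at two sites could be seen there.

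The simulation also shows known properties of the test under assumed site sizes and shifts. That is fair. The direction follows from the formula, but the percentages depend on the assumptions.

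What remains is that the named test and its printed null are incompatible in a specified analysis, whichever of the two was intended.

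**Conclusion.** The point holds as a minor error in the plan as written. For continuous items in the third set, the test named does not test the null stated, and it is not the counterpart of Breslow-Day. If its result were read as a statement about homogeneity, it would usually be significant when all sites share the same non-zero difference and would miss differences in opposite directions. When all sites agree on no difference it rejects at about the nominal 5%, so the misreading needs a real common effect. The sizes quoted rest on assumed site splits, discontinuation rates, normal responses and shifts of 0.4 or 0.8 SD, none of which the documents give.

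The reach is limited to illustrative baseline risk-behavior analyses. No efficacy or safety endpoint changes.

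**What to change.** In SAP 11 and the Figure 41 and 42 notes:

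1. As the continuous counterpart of Breslow-Day, test the study-status-by-site interaction on ranks across all three sites (2 df). The null is that the study-status difference is the same at every site. A Q test on the within-site Mann-Whitney effects would serve the same purpose.
2. If Van Elteren's test is kept, state its null as no difference by study status within sites, stratified by all three sites.
3. Replace the reference to two sites with all sites.
4. In the second bullet, change the Wilcoxon null to equality across study status within each site.
5. Name the continuous-item tests and their symbols in the figure notes. Leave the Breslow-Day flag as it is.

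The cost is a few lines of SAP text, the figure notes and one additional procedure call. No new data are needed.

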12. REPORTING CONVENTIONS

P-values ≥ 0.001 and ≤ 0.999 will be reported to 3 decimal places; p-values less than 0.001 will be reported as “<0.001”; p-values greater than 0.999 will be reported as “> 0.999”. The mean, median, standard deviation, and any other statistics other than quantiles, will be reported to one decimal place greater than the original data. Quantiles other than the median will use the same number of decimal places as the original data. Proportions will be presented as two decimal places; values <0.01 will be presented as “<0.01”. Percentages will be reported to the nearest whole number; values < 1% will be presented as “<1”. Estimated parameters, not on the same scale as raw observations (e.g. regression coefficients) will be reported to 3 significant figures.

13. TECHNICAL DETAILS

SAS version 9.4 or above will be used to generate all tables, figures and listings.

14. SUMMARY OF CHANGES IN THE CONDUCT OF THE STUDY OR PLANNED ANALYSES

The DSMB met on April 29, 2014 for a Data Review Meeting for a routine safety review. The DSMB recommended the sample size be increased to 450 subjects to replace dropout subjects. The protocol was amended on October 29, 2014 to version 7.0 to increase enrollment from 344±8 to 450±8 and extended the study duration from 47 to 54 months.

The DSMB met on September 2, 2015 for a Data Review Meeting and to review aggregate endpoint and enrollment data. The objective of this meeting was to conduct a blinded examination of progress towards the statistical information goal and to decide whether to recommend an extension of the enrollment period. The DSMB identified no safety concerns and recommended that the study continue as per the protocol. They also recommended that an 85 percent power with a two sided confidence interval was maintained and that enrollment should continue until 540 subjects are enrolled. The protocol was amended on October 6, 2015 to Version 9.0 to increase enrollment from 450±8 to 540±8 and extended enrollment from 54 to 63 months.

The definition of incident HCV infection for exploratory endpoint 1 in this SAP differs slightly from the definition in the protocol. In this SAP, two definitions of incident HCV infection are used: one which incorporates HCV RNA results only, and one that utilizes the anti-HCV testing results (see Section 3.3.3).

A number of exploratory analyses of the efficacy, immunogenicity, and risk behavior data were added to supplement the outcome measures defined in the protocol.

The protocol uses the terms “primary infection”, “acute infection”, and “incident infection” to describe the incident infection of HCV. This SAP replaces these terms with “incident infection”.

